As with cetuximab and other EGFr inhibitors, the most commonly reported side effects of panitumumab are dermatological. In a phase II trial in pretreated metastatic colorectal cancer, skin toxicity was reported by almost all subjects (95%), and reached NCTC Grade 3 in 7%.²³ Also in common with cetuximab, hypomagnesaemia has been reported in some trials. Routine monitoring was not conducted in the early clinical studies, so the incidence of asymptomatic hypomagnesaemia is not yet clear. However, grade 3 or 4 hypomagnesaemia has been reported through serious adverse event notifications in 7 of 1100 (0.6%) subjects receiving panitumumab to date. Overall the most commonly reported treatment-related side effects are fatigue (28%), diarrhoea (22%), nausea (16%), stomatitis (14%), anorexia (12%) and vomiting (7%). Grade 3 events were reported for fatigue (3%), diarrhoea, nausea and vomiting (reported at 1% each). Intensive cardiac monitoring was undertaken in the early clinical trials with panitumumab, including MUGA and cardiac enzyme monitoring in 331 patients, but no evidence of cardiotoxicity was observed (see table 1).²⁴

From the start of panitumumab clinical studies to 19 June 2005, 1575 patients were exposed. From 20 June 2004 to 19 June 2005, 4 related hypersensitivity events (SUSARs) were reported. Routine pre-medication is not recommended, but intervention is required when clinically indicated (e.g. i.v. steroids; antihistamines; adrenaline; oxygen, etc).

Table 1 AE's observed in a trial of monotherapy in mCRC (failed irinotecan +/- oxaliplatin):

All Patients (N = 148)	All AES	Grade 3	Grade 4
Skin related			
Any Skin Toxicity	141 (95%)	11 (7%)	0 (0%)
Rash	119 (80%)	5 (3%)	0 (0%)
Pruritus	50 (34%)	2 (1%)	0 (0%)
Dry skinDermatitis	38 (26%)	0 (0%)	0 (0%)
acneiform	24 (16%)	0 (0%)	0 (0%)
Skin desquamation	19 (13%)	0 (0%)	0 (0%)
Skin disorder	18 (12%)	0 (0%)	0 (0%)
Erythema	16 (11%)	0 (0%)	0 (0%)
Paronychia	16 (11%)	0 (0%)	0 (0%)
Rash macular	15 (10%)	0 (0%)	0 (0%)
Skin fissures	14 (9%)	1 (1%)	0 (0%)
Rash maculo-papular	11 (7%)	0 (0%)	0 (0%)
Rash papular	10 (7%)	0 (0%)	0 (0%)
Rash pruritic	9 (6%)	0 (0%)	0 (0%)
Dermatitis exfoliative	8 (5%)	0 (0%)	0 (0%)
Other			
Fatigue	41 (28%)	4 (3%)	0 (0%)
Diarrhoea	32 (22%)	1 (1%)	0 (0%)
Nausea	23 (16%)	1 (1%)	0 (0%)
Stomatitis	21 (14%)	0 (0%)	0 (0%)
Anorexia	18 (12%)	0 (0%)	0 (0%)
Vomiting	10 (7%)	2 (1%)	0 (0%)

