- There will also be some patients randomised under the Protocol Version 1.0 who have received IrPan and whose *K-RAS* status is determined retrospectively to be mutant or unknown. These patients will be considered in a separate exploratory comparison of efficacy using a sensitive outcome measure (proportion of patients progression-free at 12 weeks) to address the question whether panitumumab impedes irinotecan sensitivity in this context and to also assess toxicity. This exploratory analysis will consider all

patients randomised to receive Ir or IrPan under Protocol Version 1.0 whose *K-RAS* status is unknown or mutant, regardless of previous anti-EGFR targeted therapy use.

Translational objectives

PICCOLO also addresses the following translational research objectives

- Does the toxicity of **Ir** and/or **IrCs** correlate with genetic variability in the enzymes involved in irinotecan's disposition pathway?
- Does **IrCs** achieve the same PK exposure (AUC) to Ir and its metabolites (SN38; SN38G) as standard-dose **Ir**? (This study in a subset of 20 patients)
- If, overall, **Pan** is effective in patients with *K-RAS* wild-type tumours, does the degree of benefit correlate with other molecular markers which may provide a basis for more refined patient selection in the future (e.g. alterations in EGFr; *B-RAF*, *MAPK*, *STAT*, *P13K*, etc)?
- Does **Pan** efficacy or toxicity (specifically the severity of skin rash) correlate with somatic alterations in the EGFr gene, or with germline variability in related genes?

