- If diarrhoea lasts > 24 hours, ciprofloxacin 500 mg bd should be added. If it lasts > 48 hours, or if the patient reports symptoms of dehydration, he/she should be admitted acutely for rehydration and further management (e.g. octreotide).
- After an episode of severe diarrhoea (e.g. requiring admission), delay until full recovery then resume at 20% reduced dose irinotecan for all subsequent cycles
- If diarrhoea from the previous cycle has not resolved by the time the next cycle is due, delay 1 week
- Hepatobiliary function
 - LFTs should be checked before each treatment cycle. Patients with serum ALP >5 x ULN or serum bilirubin in the range 1.5-3 x ULN require a 50% dose reduction of irinotecan. If the LFTs subsequently improve to below these limits, full-dose treatment may be resumed
 - Patients with serum bilirubin >3 x ULN should not receive irinotecan. If bilirubin subsequently falls, treatment may be resumed as above.
- Renal function
 - At the time of trial entry renal function must satisfy entry criteria. Subsequently re-check serum creatinine at each cycle. The patient should not receive treatment if estimated GFR falls below 30 ml/min.
- Hypomagnesemia Management
 - Plasma magnesium should be checked prior to each cycle. If below 0.7 mmol/l, start oral magnesium supplements (initially, we recommend oral Magnaspartate® [KoRa Healthcare], one 10mmol sachet t.d.s.). Serum magnesium should be maintained above 0.4 mmol/l at all times.
- Panitumumab dermatological toxicity
 - Over 90% of patients treated with panitumumab in previous trials developed skin or nail side-effects, usually a mild-to-moderate acneiform rash, similar to that seen during cetuximab therapy. This reached NCI CTC Grade 3 in 7% and resulted in discontinuation of the drug in 1% of patients.
 - All patients allocated to receive panitumumab should be forewarned that they are very likely to develop a rash. At the first development of a rash we recommend:
 - start an oral tetracycline, e.g lymecycline 408 mg b.d.
 - start topical emollients (e.g. E45®) and bath additives (e.g. Hydromol®).
 - Skin toxicities will be recorded as adverse events on the Treatment Case Report Form and will be graded using a modified version of NCI CTC version 3.0, as detailed in Appendix 2.

The following guidelines should be used for adjusting panitumumab in the event of skin or nail toxicity:

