8.2 Operational definition and reporting adverse events

From the first administration of trial treatment until 3 weeks after the last trial drug administration, all toxicities related to the underlying colorectal cancer or its treatment, whether observed by the investigator or reported by the patient, will be collected and recorded on a Case Report Form (CRF) following each cycle of treatment. The CTRU will provide details of all toxicities to the Data Monitoring and Ethics Committee (DMEC) for their review on a yearly basis.

Specifically, known toxicities associated with irinotecan, ciclosporin and panitumumab, as identified from the most recent Summary of Product Characteristics for irinotecan and ciclosporin, and the most recent panitumumab Investigator Brochure will be collected. The following will therefore be included:

- Diarrhoea
- Nausea
- Vomiting
- Constipation
- Headache
- Lethargy
- Alopecia
- Dizziness
- Skin toxicity
- Abdominal pain
- Pyrexia
- Anaemia
- Neutropenia

- Thrombocytopenia
- Infection
- Nail toxicity
- Plus any other reported side-effects following each cycle of treatment of CTC grade ≥ 3

The following infusion related toxicities will also be collected:

- Fever
- Chills
- Respiratory
- Bradycardia/cardiac arrest
- Generalised urticaria
- Diarrhoea
- Arthralgia/myalgia
- Rigors/shakes
- Hypotension
- Plus any other reported infusion related toxicities following each cycle of treatment CTC grade ≥ 2

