10.2 Secondary Endpoints

Ir vs IrCs comparison

- Proportion of patients free from treatment failure at 12 weeks
- Overall survival (OS) from randomisation
- Research nurse-assessed toxicity (NCI-CTC[V3] grades): maximum toxicity grade per patient; rate per cycle; all-cause mortality within 60 days of randomisation; toxicity of primary interest is grade 3+ diarrhoea within 12 weeks of randomisation;

Ir vs IrPan comparison (patients with wild-type K-RAS status not previously receiving an anti-EGFR targeted therapy)

- Proportion of patients progression-free 12 weeks from randomisation.
- Research nurse-assessed toxicity (NCI-CTC[V3] grades): maximum toxicity grade per patient; rate per cycle; all-cause mortality within 60 days of randomisation;

Ir vs IrCs and Ir vs IrPan (patients with wild-type K-RAS status not previously receiving an anti-EGFR targeted therapy) comparisons

- Progression-free survival (PFS) from randomisation
- Best response by RECIST criteria within 1-year follow-up from randomisation
- Patient-assessed symptom/QL/PA scores at 12 and 24 weeks

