Kaplan Meier curves for progression-free survival will be calculated, and the difference between the treatment groups compared using a two-sided log-rank test. Survival will also be compared using multivariate modelling, Cox's Proportional Hazards model if appropriate, to adjust for the minimisation factors and other important prognostic factors. HRs and corresponding 95% CIs will be presented. Sensitivity analysis will be considered to account for missing data for PFS analysis.

Patients' best response rate⁴² will be assessed by calculating the 95% CI of the difference in response rates between the two treatment groups. In addition, a two-sided chi-squared test for trend (or appropriate version) and logistic regression, to adjust for the minimisation factors and other prognostic factors will be performed. Sensitivity analyses will be conducted to allow for any deaths from causes other than colorectal cancer.

Quality of life will be summarised using adjusted for baseline mean scores and 95% CIs for each EORTC QLQ-C30 domain, obtained from a multi-level repeated measures model, assuming data to be missing at random. Missing data patterns will be examined carefully, and if missing data patterns suggest data are missing not at random, analyses will also be carried out using pattern-mixture models, and data summarised using the Standardised Area Under the Curve. The MRC treatment value/acceptability supplement will be summarised descriptively with bar charts and summary tables for each question. The mean adjusted for baseline total Dermatology Life Quality Index score and scores for each domain will be presented with corresponding 95% confidence intervals.

To assess toxicity, the maximum grade per patient, rate per cycle and all cause mortality within 60 days of randomisation will be summarised descriptively for each treatment group. Reasons for stopped treatment will be summarised.

It is possible that the presence of skin rash may be associated with the clinical effectiveness of anti-EGFr therapies⁴³. For exploratory purposes it is therefore planned to examine the possibility that the treatment effect, as measured by best response rate, differs according to grade of acneiform rash. Best response rate will be assessed using ordered logistic regression adjusting for treatment, grade of skin toxicity and their interaction.

Ir vs. IrPan comparison (patients with wild-type K-RAS status previously receiving anti-EGFR targeted therapies)

Exploratory Analysis

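### The exploratory rash analysis conditions on a post-randomisation effect of panitumumab, so its treatment-by-rash interaction is not effect modification, and its other coefficients are biased if rash is counted over all treatment

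*Protocol*

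**What the plan says.** The analysis stands in Section 12 of the protocol, at the end of the secondary-endpoint text for wild-type patients without prior anti-EGFR therapy. Its status is clear: "For exploratory purposes it is therefore planned to examine the possibility". The question is whether "the treatment effect, as measured by best response rate, differs according to grade of acneiform rash", and the model is fixed: "Best response rate will be assessed using ordered logistic regression adjusting for treatment, grade of skin toxicity and their interaction".

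Four other places bear on it:

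- Section 6.4: "Over 90% of patients treated with panitumumab in previous trials developed skin or nail side-effects". Section 1 reports skin toxicity of any grade in 95% of 148 patients on single-agent panitumumab.
- Section 8.2: toxicities "will be collected and recorded on a Case Report Form (CRF) following each cycle of treatment".
- Section 6.3: patients with response or stabilisation are offered treatment until progression or toxicity. Patients on IrPan keep receiving panitumumab during planned breaks.
- Section 10.2: the outcome is "Best response by RECIST criteria within 1-year follow-up from randomisation".

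Section 12 gives the rash model no time window and no landmark. It calls the covariate acneiform rash in one sentence and skin toxicity in the next. Appendix 2 grades acneiform rash separately from nail changes, erythema, pruritus, non-acneiform rash and ulceration.

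**The concern.** There are two separate problems.

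**The covariate is a product of treatment.** A treatment-by-covariate interaction describes effect modification when the covariate is fixed before randomisation. Here the grade is largely produced by one arm. IrPan patients at grade 2 are those whose skin reacted to panitumumab. Ir patients at grade 2, if there are any, have rash for another reason. The two groups are not exchangeable, so the contrast between them is not a treatment effect in a subgroup. No choice of rash window changes that.

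**Time on treatment links rash and response.** Best response is read over a year, treatment continues while it helps, and toxicity is recorded each cycle. If the covariate is the maximum grade over all treatment, a patient who progresses early has few cycles in which to record rash and one who benefits has many. Benefit then raises recorded rash, rather than the reverse.

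At stake is the reading that rash marks who benefits from panitumumab. The fitted model cannot support that reading and may appear to.

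**Working it through.** The protocol gives no sample size, power or error rate for this analysis, so there is no planned figure to reproduce. The check has three steps.

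**1. Direction of the accumulation bias, by hand.** Cycles are 3-weekly (Section 6.2) and scans 12-weekly (Section 5.3). Progression by the first scan allows about 12/3 = 4 cycles. A patient with stable or responding disease treated to the second scan has about 24/3 = 8. Let *q* be the chance of no graded rash in a cycle, the same for everyone.

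- Odds of rash after *n* cycles = (1 − q^n)/q^n.
- Odds ratio, 8 against 4 cycles = [(1 − q^8)/q^8] / [(1 − q^4)/q^4] = 1 + 1/q^4.
- This exceeds 2 for any *q* below 1. With an assumed 15% per cycle (q = 0.85), the proportions are 1 − 0.85^8 = 0.73 and 1 − 0.85^4 = 0.48, and the odds ratio is 1 + 1/0.522 = 2.9.

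This contrasts early progressors with patients who continue. It does not contrast responders with all non-responders, because stable patients also continue.

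**2. The planned model under the null.** Simulation with 240 per arm (Section 11.1) and 500 runs per scenario. Response was identically distributed in both arms in these null runs: 35% progression, 55% stable, 10% response. This matches the roughly 65% progression-free and under 10% responding that Section 10.4 gives for standard therapy. Rash was unrelated to response except through cycles received. The following are assumptions, because the protocol does not give them:

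- cycles received: 1 to 4 with progression, more than 4 otherwise, capped at 17;
- per-cycle rash hazard on IrPan: 0.25 to 3.0;
- Ir patients with rash: about 1% to 27%.

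The model had treatment, grade and their interaction, with grade as the maximum over all treatment.

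| Quantity (true OR = 1) | Median OR | Falsely significant |
|---|---|---|
| Rash-response slope within IrPan, per grade | 2.6 to 3.6 | 95% to 100% of runs |
| Treatment effect at grade 0 | 0.18 to 0.36 | 99% to 100% |
| Interaction per grade, Ir rash also accumulating | 0.99 to 1.5 | positive in 0.6% to 15% |
| Interaction per grade, Ir rash not depending on time | 2.6 to 3.3 | positive in 21% to 74% |

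The nominal rate for a false positive in one direction is 2.5%. The grade 0 result arises because IrPan patients without rash are mainly early progressors, whereas most Ir patients are at grade 0 whatever their outcome.

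Precision of the interaction: with about 1% of Ir patients having rash, the standard error of the log odds ratio reached 1.10 per grade. The 95% limits then lie a factor of exp(1.96 × 1.10) = 8.6 either side of the estimate.

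**3. An early window.** Two of these scenarios were rerun with rash counted only over the first two cycles, among patients who received at least two.

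- Slope within IrPan: OR 0.97 to 0.98 per grade, significantly positive in 1.6% to 3.0% of runs. The false association is gone.
- Interaction: significant in either direction in 4.8% to 6.4% of runs (nominal 5%). Its standard error was still 0.72 to 0.78, a factor of exp(1.96 × 0.72) = 4.1 to exp(1.96 × 0.78) = 4.6 each way.

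**The case against.** The protocol labels the analysis exploratory, speaks only of a possible association, and lists it in none of the endpoint sections. That stands, and it keeps the severity low.

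No rash window is stated, and an analysis plan that is not shown could set one. This also stands. The missing window is not itself the fault, and the accumulation bias is conditional on grade being counted over all treatment. The maximum grade per patient in Section 12 belongs to the separate descriptive toxicity summary. The exchangeability problem remains, because the protocol itself fixes the interaction model.

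The Ir-arm rash rate is unknown. Section 8.7 lists mild cutaneous reactions for irinotecan, and a broad skin-toxicity covariate would pick up more than acneiform rash. So sparse Ir cells are plausible rather than established.

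Section 6.4 withholds, reduces or stops panitumumab for severe skin toxicity, which works against simple accumulation and was not simulated. It may weaken the bias, although a maximum already recorded cannot fall.

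Two stronger readings are tempting. A reader might infer that the interaction test is bound to show a rash-benefit link where none exists. The results do not support that: its false-positive rate ran from about 1% to 74% according to assumptions that the protocol cannot settle, and with little Ir rash the term is mainly uninformative. A reader might also extend the point to the translational objective in Section 2 on rash severity. That objective relates rash to EGFr gene alterations and germline variability, which is a different question.

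**Conclusion.** The point holds in a limited form. The treatment-by-rash interaction does not estimate effect modification under any rash window, because the covariate arises after randomisation and mainly from one arm. It will also be very imprecise if few Ir patients have graded rash.

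If grade is the maximum over all treatment, the rash-response association within IrPan is biased upwards and the treatment contrast at grade 0 is biased against IrPan. The interaction can, but need not, be falsely positive. The sizes shown rest on assumed rash hazards, Ir-arm rash rates and cycle counts. The direction follows from per-cycle recording and from treatment that continues with benefit.

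Severity is low: no primary or secondary conclusion of the trial depends on this analysis.

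**What to change.** Replace the interaction model with a landmark analysis in IrPan patients only:

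- **Covariate:** maximum acneiform-rash grade by Appendix 2 in a fixed early window, for example the first two cycles timed from first treatment (six weeks at the planned interval). Use that one covariate name throughout.
- **Population:** IrPan patients alive, still in follow-up and without clinically documented progression at the landmark. Treatment may start up to 14 days after randomisation, so this landmark falls 6 to 8 weeks after randomisation. The first scheduled reassessment scan is at 12 weeks, so radiological freedom from progression cannot be required at the landmark.
- **Outcome:** best response at or after the 12-week scan, and overall survival from the landmark.
- **Reporting:** an association within IrPan, with a statement that it is not evidence that rash modifies the benefit of panitumumab.

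The cost is a change of wording in Section 12 and the analysis plan. Toxicity is already recorded each cycle, and Section 6.4 has skin toxicities graded by Appendix 2. Confirm that the case report form keeps the acneiform grade separate. The downside is that patients who fail before the landmark drop out of this exploratory analysis.

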PICCOLO is a large randomised trial designed to address both of these modifications, while at the same time acquiring translational scientific information to further refine and direct these treatments in the future. A common control arm of standard single-agent irinotecan will be compared, on the one hand, with ciclosporin-modulated irinotecan and, on the other, with irinotecan plus panitumumab.

The large majority of patients entering PICCOLO will not have received a prior EGFR-inhibiting drug. However, the trial is open to patients following first-line treatment in COIN, one-third of whom will have received cetuximab. These anti-EGFR targeted therapy pre-treated patients will not be included in the primary +/- panitumumab phase III efficacy comparison, but will provide the opportunity to explore, in a randomised phase II analysis, the possibility that EGFR blockade contributes to the efficacy of second-line chemotherapy independent of its use during first-line treatment.

On this basis, PICCOLO opened to recruitment in December 2006 as a 3-arm Randomised Controlled Trial (RCT), with all patients randomised, in equal proportion, to the three study arms **Ir** (standard single-agent irinotecan), **IrCs** (irinotecan at 40% standard dose in combination with ciclosporin), and **IrPan** (standard irinotecan in combination with panitumumab).

K-RAS Mutations and anti-EGFR mAb therapy (section added for Protocol Version 3.0)

Following initiation of the PICCOLO Trial as a 3-arm randomised trial, new data have emerged to suggest that patients can benefit from the application of a molecular selection strategy. This new data necessitates a modification of the original PICCOLO trial design.

K-RAS, the human homolog of the Kirsten rat sarcoma-2 virus oncogene, encodes a GTP-binding protein that acts as a self-inactivating signal transducer by cycling from GDP- to GTP-bound states in response to stimulation of cell surface receptors including EGFR.^{26,27} Certain codons in *K-RAS* (12, 13 and 61) are common sites of mutations that yield constitutively active protein.^{28,29} Such mutations are found in approximately 30-50% of colorectal cancers.³⁰ The presence of mutant *K-RAS* in lung and colorectal cancers is a poor prognostic factor,^{30,31} and several reports from non-randomised series suggested association with lack of response to EGFR inhibitors.^{32,33}

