Since previous anti-EGFR targeted therapy use is of no concern for the Ir vs. IrCs comparison, this analysis will include all patients randomised to receive either Ir or IrCs under Protocol Version 1.0, and all patients randomised to receive either Ir or IrCs via the Ir vs. IrCs randomisation in this amended protocol, regardless whether or not they have previously used anti-EGFR targeted therapy.

The two primary comparisons of Ir vs. IrCs and Ir vs. IrPan are essentially two independent comparisons⁴¹. We therefore aim to recruit 480 patients who have wild-type *K-RAS* status and who have not previously received an anti-EGFR targeted therapy (240 patients per arm) to the Ir vs. IrPan comparison. However, dependent upon the proportion of patients with unknown *K-RAS* status, there may be some over-recruitment to this comparison. We expect approximately 15% of all patients recruited to this comparison to have previously received an anti-EGFR targeted therapy therefore the expected sample size for the exploratory analysis of Ir vs. IrPan for those patients previously receiving an anti-EGFR targeted therapy (and who have wild-type *K-RAS* status) is approximately 86 patients (43 patients per arm of Ir/IrPan).

K-RAS status

We expect that the split between mutant *K-RAS* status and wild-type *K-RAS* status will be approximately 42:58, and that approximately 15% of patients will have unknown *K-RAS* status. The proportion of patients with unknown status will be monitored as this figure may vary. Only patients with wild-type *K-RAS* status will be randomised to the Ir vs. IrPan comparison. There will, however, be some patients randomised to IrPan via protocol Version 1.0 who will have either mutant or unknown *K-RAS* status. We anticipate that approximately 167 mutant or unknown *K-RAS* status patients will have been randomised to receive either Ir or IrPan under Protocol Version 1.0, of whom approximately 19 will have previously received an anti-EGFR targeted therapy. An exploratory analysis will be carried out on these patients.

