11.2 Planned Recruitment Rate

Target recruitment is 3 years. A total of 494 patients have been recruited under Protocol Version 1.0, therefore approximately 830 patients are still to be recruited in order to achieve the required sample size: an average of 46 per month (with 18 months recruitment remaining). Given that accrual to FOCUS was 60-65 patients per month, we feel this goal is realistic. Patients in the ongoing FOCUS2 trial (460 patients) may be eligible for PICCOLO after progression, as will patients in COIN (2400 patients). Recruitment will stop when 480 patients who have not previously received an anti-EGFR targeted therapy and who have wild-type *K-RAS* status have been recruited to the Ir vs. IrPan comparison, and when 750 patients have been recruited to the Ir vs. IrCs comparison.

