The proportion of patients progression-free at 12 weeks from randomisation will be summarised for both the Ir and IrPan arms. 95% confidence intervals will also be reported.

To assess toxicity, the maximum grade per patient, rate per cycle and all cause mortality within 60 days of randomisation will be summarised descriptively for each treatment group. Reasons for stopped treatment will be summarised.

Ir vs. IrPan comparison (patients randomised to receive Ir or IrPan under Protocol Version 1.0 who have mutant or unknown K-RAS status, regardless of previous anti-EGFR targeted therapy)

Exploratory Analysis

The proportion of patients progression-free at 12 weeks from randomisation will be summarised for both the Ir and IrPan arms. 95% confidence intervals will also be reported.

To assess toxicity, the maximum grade per patient, rate per cycle and all cause mortality within 60 days of randomisation will be summarised descriptively for each treatment group. Reasons for stopped treatment will be summarised.

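### The exploratory Version 1.0 Ir vs IrPan analysis pools K-RAS mutant with K-RAS unknown patients, which dilutes any efficacy harm from panitumumab in mutant disease (minor)

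*Protocol*

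**What the plan says.** Section 2 sets aside Version 1.0 patients on Ir or IrPan whose K-RAS status proves mutant or unknown, for a separate exploratory efficacy comparison at 12 weeks. Its purpose is "to address the question whether panitumumab impedes irinotecan sensitivity in this context and to also assess toxicity". Section 10.3 repeats this population, and section 12 heads the analysis "Ir vs. IrPan comparison (patients randomised to receive Ir or IrPan under Protocol Version 1.0 who have mutant or unknown K-RAS status". None of the three places gives a mutant-only summary.

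For the analysis itself, section 12 says that the proportion progression-free at 12 weeks "will be summarised for both the Ir and IrPan arms. 95% confidence intervals will also be reported". It does not name the between-arm difference. Section 12.1 adds that the exploratory endpoints get no formal statistical analysis.

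On composition, section 11.1 states: "We expect that the split between mutant *K-RAS* status and wild-type *K-RAS* status will be approximately 42:58", and "approximately 15% of patients will have unknown *K-RAS* status". It anticipates about 167 mutant or unknown patients on Ir or IrPan from Version 1.0, about 19 of them previously given anti-EGFR therapy. Section 3 describes unknown status as assay failure or lack of tissue. It also says that Version 1.0 patients are typed retrospectively, subject to consent for tissue retrieval.

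**The concern.** The analysis asks whether panitumumab works against irinotecan. The background (section 1, K-RAS subsection) raises possible antagonism for mutant tumours only, and section 11.1 powers the wild-type comparison for a 30% reduction in hazard. An unknown result says nothing about the tumour, so the unknown group should contain both types. The pool thus mixes patients in whom harm is the question with patients in whom benefit is expected, and the mixture pulls the estimate away from harm.

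From the redesign onward, mutant and unknown patients are randomised only between Ir and IrCs (sections 3 and 5.2). The Version 1.0 patients are therefore the trial's only randomised evidence on panitumumab in known-mutant disease. A pooled figure does not estimate the effect in those patients. Arm-level proportions alone also leave the reader to derive the contrast that answers the question.

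**Working it through.** **Inputs from the protocol**
- Section 11.2: "A total of 494 patients have been recruited under Protocol Version 1.0".
- Section 1: Version 1.0 allocation "with all patients randomised, in equal proportion, to the three study arms".
- Section 11.1: mutant to wild-type 42:58; 15% unknown; 63.3% progression-free at 12 weeks on irinotecan; hazard ratio 0.70 for overall survival in wild-type patients.

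**Assumptions, not in the protocol**
- Untyped patients split 42:58 like typed ones.
- The 63.3% applies to this set.
- The harm in mutant patients takes illustrative sizes of 5 to 20 points.
- The wild-type effect is either zero or the 0.70 carried over to 12-week progression-free status.

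**Step 1: reproduce the protocol's 167**
- Ir + IrPan = 494 × 2/3 = 329.3
- Mutant = 329.3 × 0.85 × 0.42 = 117.6
- Unknown = 329.3 × 0.15 = 49.4
- Total = 167.0, which matches the stated figure

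**Step 2: wild-type share of the pool**
- Wild-type among unknown = 0.58 × 49.4 = 28.7
- Share of pool f = 28.7 / 167.0 = 17.2%, about one in six of the pool (58% of the unknown group)
- With unknown rates of 10%, 20% or 30% in place of 15%, f is 12%, 22% or 29%

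**Step 3: dilution**

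Pooled effect = (1 − f) × mutant effect + f × wild-type effect.

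Wild-type benefit under the carried-over hazard ratio: 0.633^0.70 − 0.633 = +9.3 points.

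| Assumed mutant harm | Share kept, wild-type effect 0 | Share kept, wild-type +9.3 |
|---|---|---|
| 5 points | 83% | 51% |
| 10 points | 83% | 67% |
| 15 points | 83% | 72% |
| 20 points | 83% | 75% |

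For a 10-point harm, the pooled effect is −8.3 points with zero wild-type effect. With the benefit it is 0.828 × (−10) + 0.172 × 9.3 = −6.7 points.

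Full cancellation needs a wild-type benefit of (1 − f)/f = 0.828/0.172 = 4.8 times the mutant harm.

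**Step 4: precision of the difference (10-point harm)**

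Half-width = 1.96 × √{[p₀(1 − p₀) + p₁(1 − p₁)]/n}, with n per arm and p₀ = 0.633.
- Mutant-only: n ≈ 59, p₁ = 0.533, half-width about 17.7 points, illustrative power (two-sided 5%) 19%
- Pool: n ≈ 83, p₁ = 0.566 (wild-type +9.3), half-width about 14.8 points, illustrative power 14%
- With zero wild-type effect, power is about 19% either way

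**The case against.** - **Cancellation.** A reader might infer that pooling hides the harm, or that opposite effects cancel. The figures do not support that. About 83% of the pool is expected to be mutant, and cancellation would need a wild-type benefit nearly five times the mutant harm. About 19 of the 167 are anti-EGFR pre-treated, and section 11.1 thinks cross-resistance possible, so the wild-type benefit may be smaller than assumed here.
- **Presumed harm.** A reader might also infer that harm is to be expected. Section 1 limits the antagonism signal to oxaliplatin with or without bevacizumab, and says it was not seen with anti-EGFR drugs alone or combined with irinotecan. The protocol asks an open question.
- **A coherent population.** The redesigned trial randomises mutant and unknown patients together, so the pool is the Version 1.0 counterpart of a group the design uses: patients not shown to be wild-type. That stands as a reason to keep the pooled row. It does not make the row an answer for mutant tumours.
- **Exploratory status.** There is no test, power or decision rule, and no primary or secondary conclusion depends on this analysis. That stands and limits the severity. A further breakdown could be left to the analysis plan, and nothing bars a mutant-only row, but the protocol itself fixes the pooled population in three places.
- **The difference is derivable.** Two proportions with arm sizes yield the difference and its interval, and the promised intervals are not expressly limited to single arms. That part of the point is small.
- **Little gain in power.** This is true: sample size is the main limit either way. Nor is the toxicity summary shown to be diluted in this way.

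**Conclusion.** The point holds as a minor one. The pooled analysis dilutes an efficacy harm in mutant patients by about 17% if panitumumab has no effect in wild-type patients. If the 0.70 hazard ratio carries over, it dilutes harms of 20 down to 5 points by about a quarter to a half. The first result rests on untyped patients splitting 42:58 and on 15% being unknown. The second also rests on the carry-over and on the illustrative harm sizes. If retrospective typing leaves more than 15% unknown, the dilution grows. Separating the groups gives an estimate that can be interpreted for mutant patients, still with wide uncertainty.

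**What to change.** In sections 2, 10.3 and 12, make the mutant-only group (about 118) the main exploratory efficacy summary for this question. Show the unknown group (about 49) separately and keep the pool (about 167) as a third row. For each, report the descriptive IrPan minus Ir difference in the 12-week progression-free proportion with its 95% CI, beside the arm-level proportions. A descriptive difference is compatible with section 12.1, since it adds no test.

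The cost is one more table from data already being collected, and a wider interval in the mutant-only row: half-width about 18 points against 15 for the pool.
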